2. Identify putative psychological mechanisms of response to CPT through pre-, mid-, and post-intervention measures of PTSD severity as well as measures of hopelessness, self-blame, and negative self-related thoughts.

Hypotheses:

NIMH Branch:

1. It is predicted that feasibility will be established by obtaining $\geq 80\%$ participant retention for the CPT course. As additional metrics of feasibility we will assess eligibility;

[†]For the NIMH branch, any historical data (i.e., information that is stable and is not expected to change over time) that has already been collected through protocol 2014-1106, we will obtain this data from the PI's database (2014-0350) and will not re-administer these assessments under the current protocol.

- participation; compliance; adherence; competence; and safety.
2. It is predicted that group CPT acceptability will be established by obtaining mean scores ≥ 27 on the CSQ-8.
 3. It is predicted that assessment collection feasibility will be established by obtaining 100% of PCL-5s at each timepoint for participants retained at that timepoint.

WPP Branch:

1. It is predicted that compared to the active control group, the CPT group will exhibit significantly greater reductions in PTSD symptom severity (primary outcome measure) as well as reductions in the severity of depression and general anxiety symptoms (secondary outcome measures) over the course of treatment.
2. It is predicted that the CPT group will exhibit greater reductions in hopelessness, self-blame, and negative self-related thoughts compared to the active control group.
 - a. Within only the CPT group, the reductions in hopelessness, self-blame, and negative self-related thoughts will precede the reduction in PTSD symptoms.
 - b. Within only the CPT group, the reduction in PTSD symptom severity will be mediated by reductions in hopelessness, self-blame, and negative self-related thoughts.

Trainee Project:

This study is part of the dissertation project of [name].

Participants:

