Specific Aim #1: Our assessment of feasibility of the interventions will be determined by measures of eligibility, participation, retention (primary measure), compliance with intervention activities, adherence to intervention elements, competence of intervention elements, and safety.

Primary Outcome Measure:

Retention will be measured as the percentage of residents attending all 12 sessions. Retention rates for CPT in non-incarcerated samples are typically 80% or less [15]; hence, our study goal is $\geq 80\%$ retention. Retention is our primary measure of feasibility for this aim.

Secondary Outcome Measures:

Eligibility will be measured as the percentage of participants who meet the full set of inclusion criteria. We will also compute the percentages of participants who are excluded for each individual criterion separately, so we are able to discern the relative impact of each criterion on study eligibility.

Participation will be measured as the percentage of eligible participants agreeing to

participate. Our study goal is $\geq 75\%$ participation of eligible participants.

Compliance will be measured as the percentage of retained participants performing intervention activities during session (e.g., attending to and contributing to the discussion); the percentage of participants completing the homework assignment each week; and the percentage of participants fully completing the pre-, mid-, and post-intervention assessment batteries. Our study goal is $\geq 80\%$ compliance of participants-retained in the study.

Adherence by the therapists will be measured by ratings of the presence or absence of five session elements (scores 0-5) by the clinical supervisors, as in previous CPT studies [16, 18]. Adherence ratings will be collected for two audiotaped group sessions out of each 12-session intervention (16.7% of sessions). Our study goal is adherence scores ≥ 4 for each session.

Competence of the therapists will be measured by ratings of the quality of session elements (scores 1-7; 1="not satisfactory", 4="satisfactory", 7="excellent") by the clinical supervisors, as in previous CPT studies [16,18]. Competence ratings will be collected for two audiotaped group sessions out of each 12-session intervention (16.7% of sessions). Our study goal is competence scores ≥ 4 for each session.

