If a participant is withdrawn by the clinician, they will be offered the option to complete study-related follow-ups. If the participant chooses not to complete the follow-up activities, they may withdraw from the study entirely.

WPP Branch Study Stopping Rules:

1. Participants who miss more than three sessions will not be allowed to rejoin the treatment group. Participants will be notified through internal mail or in person following their return to group.
2. Participants will be removed from group if they exhibit self-harming behaviors requiring clinical observation.
3. Lack of engagement as assessed by continually not paying attention during group, not completing homework, not taking notes during group, and not engaging in discussion.

Risk/Benefit Assessment

Known Potential Benefits to the Subjects:

Participants may experience an improvement in how they are feeling after completing a therapy group. However, we cannot promise this will happen. Participation in this research study may benefit other people in the future by helping us learn more about how to treat PTSD in currently incarcerated individuals.

Known Potential Risks:

Some subjects may find the questionnaires to be boring or tiring. They may also feel uncomfortable with sharing information about their emotions and personality.

While completing the therapy groups, some people may feel upset or emotional talking about their feelings and experiences with others. Participants may also experience temporary increases in mental health symptoms, like depression, anxiety, sleep disturbances, and other PTSD symptoms [56-58;54] Peterson et al. (2022) report that the most common adverse events in their CPT treatment for active-duty military and veteran participants with PTSD were mental health symptoms, including, nightmares (7.5%), sleep difficulty (5.8%), depression (5.0%), anxiety (4.2%), and irritability (4.2%). Similarly, Sloan et al. (2022) report that the most common adverse events in their CPT treatment for active service military members with PTSD were mental health symptoms such as anxiety, depression, and sleep disturbances. In rare cases, such symptoms can

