Regarding criterion (i), this study is designed to identify psychological and affective factors that may predispose a person to criminal behavior and incarceration in order to effectively design and implement treatment programs. Specifically, PTSD severity has been linked to increased risk of recidivism, and trauma is a hypothesized precursor to criminality [2,3,10].

Statistical Considerations:

NIMH Branch:

The primary goal of this study is to establish feasibility of the target intervention (CPT). Hence, we base our power analysis on the “retention” data collected Specific Aim #1 (i.e., the percentage of participants completing the CPT intervention). A sample size of $n = 32$ for the CPT group will provide 80% power to perform a one-sided test where the null hypothesis is 60% retention (approximately the lowest retention rate reported in previous CPT trials, versus the alternative hypothesis of 80% retention (our study goal), with a Type I error of 5%.

WPP Branch:

The primary goal of this study is to examine efficacy of the target intervention (CPT). Therefore, we will use the same target sample size ($n = 32$) used to establish feasibility of the target intervention, as this reflects the number of participants needed to conduct powered analyses based on the lowest retention rate reported in previous CPT trials.

Both the NIMH and WPP branches satisfy this condition with sample sizes of $n = 60$ for the CPT groups and sample sizes of $n = 60$ for control groups (WPP branch only).

REFERENCES

1. James, D. J., Glaze, L. E., & Statisticians, B. (2006). *Bureau of Justice Statistics Special Report Highlights Mental Health Problems of Prison and Jail Inmates*.
4. Kessler, R. C., Wai, T. C., Demler, O., & Walters, E. E. (2005). Prevalence, severity, and comorbidity of 12-month DSM-IV disorders in the National Comorbidity Survey Replication. In *Archives of General Psychiatry* (Vol. 62, Issue 6, pp. 617–627). <https://doi.org/10.1001/archpsyc.62.6.617>

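### NIMH branch: the primary feasibility measure is scored as attendance at all 12 sessions in one section and described as completing the intervention in another, so a well-retained course could be called not feasible

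*Combined protocol and SAP*

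**What the plan says.** Four NIMH places bear on retention.

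- **Measurement of Specific Aims, Specific Aim #1 (Primary Outcome Measure):** "Retention will be measured as the percentage of residents attending all 12 sessions". The 80% goal follows, taken from retention rates in non-incarcerated CPT samples. The summary closing this aim makes at least 80% retention a condition of feasibility.
- **Statistical Considerations:** the sample size rests on the Aim #1 retention data, glossed as "i.e., the percentage of participants completing the CPT intervention". The plan is to "perform a one-sided test where the null hypothesis is 60% retention", a figure described as "approximately the lowest retention rate reported in previous CPT trials", against 80%, with one-sided 5% error, 80% power and n = 32.
- **Hypotheses:** feasibility is predicted by "obtaining $\geq 80\%$ participant retention for the CPT course".
- **Specific Aim #3:** a participant is retained at a timepoint, which reads as still being in the study.

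The denominator also varies: residents in the Aim #1 definition, participating participants in its summary. No NIMH text gives an absence allowance, a make-up rule or a definition of completing. The only tolerance for absences is under WPP Branch Study Stopping Rules: "Participants who miss more than three sessions will not be allowed to rejoin the treatment group".

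**The concern.** The primary NIMH objective is decided by one percentage, and the plan gives two ways to count it. Someone who attends 11 sessions and finishes the course fails under Specific Aim #1 and, on an ordinary reading, succeeds under Statistical Considerations. An analyst could follow either sentence and reach opposite conclusions from the same data.

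The direction of the difference is certain. Everyone who attends all 12 sessions has also completed the course, so the all-12 rate is at or below the completion rate. If the 80% and 60% benchmarks were counted as course completion, the all-12 rate is being held to a standard set for a looser quantity.

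There is a knock-on effect. The compliance goal is set among retained participants. If retained there carried the Aim #1 definition, compliance would be measured only in perfect attenders, a favourably selected group.

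**Working it through.** **Inputs from the plan.** 12 sessions; null 0.60; alternative and goal 0.80; one-sided 5%; n = 32 (Statistical Considerations); 72 NIMH participants (NIMH branch description).

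**Assumptions, not in the plan.** Let c be the share who stay to the end, and q their attendance per session, taken from 0.95 to 0.99. Absences are either independent or clustered within person (beta-binomial, intraclass correlation ρ from 0.1 to 0.5).

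**1. The plan's own sample size.**
- Score approximation: [1.645·√(0.6·0.4) + 0.842·√(0.8·0.2)]² / 0.20² = 32.6.
- Arcsine approximation: 31.6, which rounds up to 32.
- Power at n = 32 by the score approximation is 79.2%.
- Exact binomial: at least 25 of 32 has error 2.5% and power 69.8%; at least 24 of 32 has error 5.7% and power 82.5%.

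The stated n = 32 reproduces, so the arithmetic is not at issue.

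**2. Independent absences.** P(attends all 12) = c·q¹².
- Attendance needed for 80% with c = 1: 0.80^(1/12) = 98.2%, or 12 × (1 − 0.982) = 0.22 missed sessions per person. With c = 0.9: (0.80/0.90)^(1/12) = 99.0%. With c = 0.8: 100%, meaning no absence by anyone who stays.
- c = 1, q = 0.95: 0.95¹² = 54.0%, below the 60% null, while 99.8% miss three or fewer.
- c = 1, q = 0.97: 69.4%, while over 99.9% miss three or fewer.
- c = 1, q = 0.99: 88.6%, which passes.
- c = 0.9, q = 0.97: 0.9 × 0.694 = 62.4%, against 90% staying to the end. The chance of observing at least 58 of 72 (80.6%) is about 0.1%; at a true rate of 90% it is over 99%.

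**3. Power when exactly 80% stay to the end** (n = 32, at least 25 needed, independent absences):

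| Counted as | True rate | Exact power |
|---|---|---|
| Course completion | 80.0% | 69.8% |
| All 12, q = 0.99 | 70.9% | 24.5% |
| All 12, q = 0.98 | 62.8% | 5.0% |
| All 12, q = 0.97 | 55.5% | 0.7% |

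**4. Clustered absences.** With a = q(1/ρ − 1) and b = (1 − q)(1/ρ − 1), P(attends all 12) = c·B(a + 12, b)/B(a, b), where B is the beta function. At q = 0.95:

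| ρ | All 12, no drop-out | Chance of ≥58/72 | All 12, 10% drop-out | Chance of ≥58/72 |
|---|---|---|---|---|
| 0.1 | 66.8% | 0.7% | 60.1% | under 0.1% |
| 0.3 | 78.8% | 42.7% | 71.0% | 4.4% |
| 0.5 | 85.5% | 90.7% | 76.9% | 28.2% |

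At q = 0.97 with no drop-out, all-12 attendance is 78.7% at ρ = 0.1 and 83.5% at ρ = 0.2.

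**The case against.** The strongest reply is that there may be only one definition. Statistical Considerations glosses the data collected under Specific Aim #1 and so points back to it. CPT here is a 12-session course, so completing it could mean attending all 12. That is a possible reading, but the plan does not state it, and the looser use of retained in Specific Aim #3 pulls the other way. The ambiguity stands.

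A reader might infer that the 80% and 60% benchmarks are course-completion rates. The documents do not establish this: they call them retention rates and do not say how the cited sources counted them.

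A reader might also infer that a well-retained course is bound to fail. That does not follow either. Attendance is not given, and at about 99% attendance with no drop-out, or with clustered absences and no drop-out, the course can pass.

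Three further replies have some force. The three-absence limit is a WPP stopping rule, not an NIMH definition of completion. The compliance wording can be read as still in the study, which softens the knock-on effect. A strict threshold also errs towards not claiming feasibility. None of these settles which count decides the primary objective.

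**Conclusion.** The point holds as an inconsistency in the primary NIMH measure with a conditional consequence. It is certain that the all-12 rate cannot exceed the completion rate, and that a single absence turns a finisher into a failure under Specific Aim #1. The size is conditional on assumed attendance. With independent absences, the rule falls below 80% unless attendance is at least 98.2% with no drop-out, or 99.0% with 10% drop-out. With no drop-out, clustering can reverse the verdict; with 10% drop-out and 95% attendance, the all-12 rate stays below 80% for every ρ examined up to 0.5. The supportable conclusion is that the rule could, and under many plausible attendance rates would, return a verdict of not feasible for a well-retained course. The wording should be fixed before analysis, because the pass or fail of the primary objective turns on it.

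**What to change.** 1. Use one definition of retention and one denominator, participants starting CPT, in Hypotheses, Specific Aim #1 and its feasibility summary, and Statistical Considerations.
2. Make the primary measure course completion, as Statistical Considerations describes it: not discontinued or withdrawn, and attending at least a minimum number of sessions chosen by the sponsor. This is an analysis definition and changes no treatment rule. The WPP three-absence limit is one option already in the protocol.
3. Confirm that the sources of the 80% goal and 60% null counted retention in that way, or restate both figures and recheck n.
4. Report all-12 attendance and the distribution of sessions attended as secondary measures.
5. State that retained, in the compliance goal, means still in the study and not perfect attendance.

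The cost is a wording change plus a check of the cited sources. Attendance is already recorded in the treatment notes after each session. The downside is a criterion more lenient than perfect attendance, which the secondary measure discloses.

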Safety will be measured through the suicidal ideation item on Beck Depression Inventory-II [34], administered at the pre-, mid-, and post-intervention assessments. Participants who endorse current suicidal ideation will be referred to mental health services within the institution.

In sum, we will consider the study successful in terms of feasibility if we meet the following thresholds for each intervention: participation rate $\geq 75\%$ of eligible participants; retention rate $\geq 80\%$ of participating participants; compliance rate $\geq 80\%$ among retained participants; adherence scores ≥ 4 ; competence scores ≥ 4 ; and $\leq 10\%$ of participating participants reporting an increase in suicidal ideation.

Specific Aim #2: Our assessment of acceptability of the interventions will be determined through measures of client satisfaction and reasons for treatment dropout.

Primary Outcome Measure: Acceptability will be measured by client satisfaction using participant scores on the CSQ-8. Other studies of CPT [44] have established acceptability of interventions using the CTQ-8 when mean scores are ≥ 27 ; hence, our study goal is scores of ≥ 27 on the CTQ-8. Client satisfaction is our primary measure of feasibility for this aim.

Secondary Outcome Measures: Reasons for discontinuation of treatment will be measured through participant self-report.

We will consider the study successful in terms of acceptability if client satisfaction mean ratings

are ≥ 27 on the CTQ-8.

Specific Aim #3: Our assessment of feasibility of assessment distribution will be determined through measures of assessment completion.

Primary Outcome Measure:

Assessment completion will be measured as the percentage of PCL-5 at each timepoint for the number of participants retained at that timepoint.

We will consider the study successful in terms of assessment distribution feasibility if 100% of PCL-5 assessments at each timepoint are completed for each participant retained at that timepoint.

WPP Branch:

Specific Aim #1: To assess preliminary efficacy, we will collect primary and secondary outcome data at the pre-, mid-, and all post-intervention time points.

Primary Outcome Measure:

PTSD symptom severity will be measured with the PTSD Checklist for DSM-5 (PCL-5) [33].

Secondary Outcome Measures:

Depression symptom severity will be measured with the BDI-II [34]. Anxiety symptom severity will be measured with the BAI [35].

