NIMH: Potential eligible participants will be identified through a research database maintained by the P.I. (2014-0350). This database includes demographic (e.g. age, race, IQ) and psychological variables (e.g., psychopathy score, substance abuse) collected during our initial screening and interviewing protocol. Participants who previously scored highly on a self-report measure of PTSD symptomology (PTSD Checklist for DSM-5 > 33 [33]) that is included in our initial screening process will be prioritized for this study. All prison studies that we conduct utilize this database to recruit eligible participants.

WPP: Potential eligible participants will be identified through the trauma treatment waitlist at the facilities. These participants have been screened for active psychosis, suicidality, and self-harm or will be identified through a research database maintained by the P.I. (2014-0350). This database includes demographic (e.g. age, race, IQ) and psychological variables (e.g., psychopathy score, substance abuse) collected during our initial screening and interviewing protocol. Participants who previously scored highly on a self-report measure of PTSD symptomology (PTSD Checklist for DSM-5 > 33^[33]) that is included in our initial screening process will be prioritized for this study. All prison studies that we conduct utilize this database to recruit eligible participants.

Study Stopping:

Participants can withdraw themselves from this study at any time. Participants may be withdrawn from the study treatment group under the following circumstances; if they endorse suicidal ideations with intent or plan and/or it significantly increases throughout the course of treatment (explained below under “Suicidality Risk”), PTSD symptoms significantly worsen over time due to treatment per participants report and clinicians’ discretion (explained below under “PTSD Symptoms Worsening”), noncompliance with treatment requirements or consistently being harmful or disruptive to other group members or the therapist, or serious adverse events directly related to treatment. In the event that one of these circumstances occurs and the participant is not withdrawn from the study based on clinician discretion, the clinician will document this circumstance and rationale. A serious adverse event is classified as life threatening, requires inpatient hospitalization, persistent or significant disability or incapacity, or is an important medical event [51].

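### NIMH branch: the compliance rate can be raised by withdrawing participants for noncompliance, because only retained participants are counted

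*Combined protocol and SAP*

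**What the plan says.** Four statements bear on this point.

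- **Compliance measure** (Measurement of Specific Aims, NIMH Branch, Specific Aim #1, Secondary Outcome Measures): "Compliance will be measured as the percentage of retained participants performing intervention activities during session". Two further components follow, "the percentage of participants completing the homework assignment each week" and completion of the assessment batteries, and these are worded for participants without the word retained. The goal sentence that closes the paragraph applies 80% to retained participants for the measure as a whole.
- **Success rule** (end of Specific Aim #1): "we will consider the study successful in terms of feasibility if we meet the following thresholds for each intervention". The list includes "compliance rate $\geq 80\%$ among retained participants" and "retention rate $\geq 80\%$ of participating participants".
- **Definition of retention** (Primary Outcome Measure of the same aim): "Retention will be measured as the percentage of residents attending all 12 sessions".
- **Withdrawal** (Study Stopping, not confined to one branch): "Participants may be withdrawn from the study treatment group under the following circumstances", and one of those circumstances is "noncompliance with treatment requirements or consistently being harmful or disruptive to other group members or the therapist". The wording is permissive. If staff keep such a person in the group, the clinician documents why.

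The plan gives no compliance rate over all starters, and no rule for how a person withdrawn for noncompliance enters the compliance measure.

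**The concern.** The denominator of the compliance rate depends on the behaviour that the rate is meant to measure. A participant who does not do the homework or take part in sessions lowers the rate while in the group. If staff withdraw that participant for this reason, the rate goes up, although nobody's behaviour has improved. Good-faith use of the withdrawal option is enough to produce this.

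The NIMH branch exists to establish feasibility, and its results will inform later work in prisons. Near the threshold, the compliance verdict would partly reflect how staff used a discretionary option, and two sites with the same participant behaviour could report different rates.

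**Working it through.** **Figures in the plan.** The documents give no expected compliance rate and no sample size for compliance. The only NIMH calculation, under Statistical Considerations, concerns retention: n = 32, 60% against 80%, one-sided 5%, power 80%. It reproduces. The normal approximation gives [1.645 × √(0.6 × 0.4) + 0.842 × √(0.8 × 0.2)]² / 0.2² = 32.6, and the arcsine version gives 31.6. That calculation does not involve the compliance denominator and is not affected.

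**Inputs.** N = 72 (NIMH Branch paragraph just before Research Design and Procedures); both thresholds 80%; retained = all 12 sessions attended. For illustration, each participant is treated as either a complier or a non-complier, although the plan has three component percentages. The counts of compliers are assumptions.

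**Formulas.** Let c be the number of compliers and k the number of non-compliers withdrawn, with no other attrition.

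- Compliance as planned = c / (72 − k)
- Retention = (72 − k) / 72
- Compliance over all starters = c / 72

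**Limit set by retention.** 0.80 × 72 = 57.6, so at least 58 must be retained and k can be at most 72 − 58 = 14.

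**Results at N = 72, no other attrition.**

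| Compliers c | c / 72 | Withdrawn k | Compliance as planned | Retention |
|---|---|---|---|---|
| 57 | 79.2%, fail | 1 | 57/71 = 80.3%, pass | 71/72 = 98.6%, pass |
| 55 | 76.4%, fail | 4 | 55/68 = 80.9%, pass | 68/72 = 94.4%, pass |
| 50 | 69.4%, fail | 10 | 50/62 = 80.6%, pass | 62/72 = 86.1%, pass |
| 47 | 65.3%, fail | 14 | 47/58 = 81.0%, pass | 58/72 = 80.6%, pass |
| 46 | 63.9%, fail | 14 | 46/58 = 79.3%, fail | 58/72 = 80.6%, pass |

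The counts that can change from fail to pass are 47 to 57. From 58 upwards compliance passes with no withdrawals (58/72 = 80.6%). At 46 or fewer, enough withdrawals to pass compliance would fail retention.

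**Other sample sizes in the documents.** At 60 (the CPT group size under Statistical Considerations) the range is 39 to 47 compliers (65.0% to 78.3%). At 32 it is 21 to 25 (65.6% to 78.1%).

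**Other attrition.** The documents do not split attrition by cause, so a range is assumed. With d lost for other reasons, also outside the denominator, the room for withdrawals is 72 − d − 58.

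| Assumed other attrition | d | Room for withdrawals | Compliers that can flip, of those left |
|---|---|---|---|
| 0% | 0 | 14 | 47 to 57 of 72 |
| 5% | 4 | 10 | 47 to 54 of 68 |
| 10% | 7 | 7 | 47 to 51 of 65 |
| 15% | 11 | 3 | 47 to 48 of 61 |
| 20% | 14 | 0 | none |

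The upper end of each range is the largest count below 80% of those left: 0.80 × 68 = 54.4, 0.80 × 65 = 52, 0.80 × 61 = 48.8.

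**The case against.** The strongest defence is that the criteria form an explicit cascade: participation among the eligible, retention among participants, compliance among the retained, with all of them required. A person withdrawn for noncompliance is not lost from view but counts as a failure of retention, the primary measure. A conditional compliance rate with a stated denominator is a legitimate description. This stands in part. Retention caps the effect, but it tolerates 14 losses of 72, so within that margin the selection remains.

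Second, the best-case room for withdrawals is unlikely to be available. Retention requires every session to be attended, so one missed session uses up a place, and the plan itself says that CPT retention outside prison is typically 80% or less. This stands: at 20% other attrition the room is gone.

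Third, the wording leaves some doubt about the denominator. Only the in-session component names retained participants. The goal sentence speaks of retention in the study, and people withdrawn by a clinician are offered study follow-ups, so they might be thought still retained. The only definition given is attendance at all 12 sessions, however, and the success rule applies retained to the whole measure. The doubt is a further reason to state each denominator.

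A reader might go further and infer that passing depends on staff decisions and not on how participants behave. The documents do not support that: withdrawal is discretionary, and outside the ranges shown it cannot turn an overall failure into a pass. Nor do they give any sign that the option would be used to improve the rate.

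**Conclusion.** The point holds in a limited form. As written, the compliance rate can be raised by withdrawing participants for noncompliance, and the retention threshold limits this without removing it. At N = 72 with no other attrition, true compliance of 65.3% to 79.2% can become a pass on both criteria. The range shrinks as other attrition grows and vanishes at about 20%. This rests on the definition of retained as all 12 sessions attended, and on a single complier status used for illustration.

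A reader might also multiply the two thresholds (0.80 × 0.80 = 64%) and conclude that feasibility could be declared with only 64% of starters complying. That product is the floor for being both retained and compliant. Someone who was transferred or missed one session may have complied fully, and the attainable minimum at N = 72 is 47/72 = 65.3%.

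Compliance is a secondary measure and the powered retention test is untouched, so this is a cheap improvement and not a flaw in the design. It is worth making because compliance is one of the thresholds for declaring feasibility.

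**What to change.** In the compliance paragraph and the summary success rule of Specific Aim #1 (NIMH Branch):

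1. Define the compliance denominator as everyone retained plus anyone withdrawn for noncompliance, and count the latter as non-compliant. In the example with 55 compliers and 4 withdrawn, the rate is then 55 / (68 + 4) = 76.4%, the same as with no withdrawals.
2. Use this denominator for both the in-session and the homework components, and state the denominator for battery completion.
3. Report battery completion over all starters only as an additional description. As the criterion, it would score transfer or release as noncompliance.
4. Keep the retained-only rate as a secondary figure.

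Study Stopping already lists the withdrawal reasons. Noncompliance and disruptive behaviour share one clause there, so the reason applied should be logged separately for each withdrawal. Treatment notes already track attendance and homework; they do not name individual in-session activity, but the planned measure needs that record in any case.

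The cost is wording, that log entry and a somewhat less favourable compliance rate. No change to the withdrawal rule, the treatment or the sample size is proposed. The change does not cover participants who stop of their own accord, whose reasons the plan already collects and can report alongside.
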